4 STUDY DESIGN

4.1 OVERALL DESIGN

The goal of this study is to assess the feasibility of the use of CGM for detection of postpartum diabetes, IGT, and IFG. Women with a diagnosis of GDM in their current or recent pregnancy will be recruited, and a Dexcom Professional CGM will be placed on postpartum day 0-3 and worn for ten days. This period of time would be less influenced by peripartum glucocorticoid use than an OGTT on hospital day 2. The CGM device will be returned at around two weeks at the routine postpartum obstetrics visits, at routine pediatric visits, or by mail. This ease of device return has the potential to greatly increase the adherence rates to postpartum testing, as compared to returning for the standard 6-12 week OGTT. The rates of CGM return, acceptability of system use by participants, sensitivity, specificity, PPV, NPV, and predictors of non-completion will be analyzed.

Visit 1: Women with a diagnosis of GDM in their current or recent pregnancy will be identified from physician referral and labor and delivery floor trackers. Inclusion criteria include diagnosis of gestational diabetes during a current or recent pregnancy and age 18 or older. Exclusion criteria include known pregestational diabetes, known skin adhesive allergy which would prevent subject from wearing a CGM, and chronic glucocorticoid use which is planned to be ongoing after labor and delivery discharge. They will be invited to participate and consented at their obstetrics or endocrinology visits during their third trimester or during admission for delivery. This visit can be performed in person or remotely. Medical history, medications, GDM diagnosis timing and values, age, race and ethnicity, education level, insurance type, parity, estimated pre-pregnancy weight and BMI, history of GDM in prior pregnancies, history of hypertension, other pregnancy complications, and family history will be recorded. If Visit 2 is planned to be performed remotely, Dexcom Pro training and supplies will be provided at this visit.

Visit 2: Visit 2 can be performed in conjunction with Visit 1 if the participant is already postpartum at recruitment or as a separate visit. It can be performed on the postpartum floor or remotely. The participant will be asked about pregnancy and delivery complications, GDM management, number of prenatal obstetric visits, estimated pregnancy weight gain, delivery weight and body mass index, gestational age at delivery, delivery method, steroid administration within the past week, fetal weight and complications, HbA1C values if available, and hemoglobin values. Participants will be asked for permission for access to review and record their future OGTT results. A Dexcom G6 Pro (or Dexcom G7 if FDA approved and available at the time of study) will be placed on an approved body site. The devices will be supplied by Dexcom at no cost to the subject. The participant will be trained on appropriate care of the sensor and removal.

Home use: Participants will wear the sensor for ten days or less if there is a sensor failure or the device is dislodged. After ten days, the participant will remove the sensor.

Visit 3: Visit 3 will occur 1-4 weeks after sensor placement. This visit can coincide with the participant's obstetrics or pediatric visit and can be performed in person or remotely. The participant will return the sensor at this visit, or mail the sensor to the study team within thirty days of placement. Postpartum complications and method of infant feeding obtained as part of normal postpartum care will be recorded. Participants will be asked whether they snack overnight and typical timing of breakfast, and the research team will determine what hour of the day would be considered fasting. If a participant is never fasting for over six hours, she will be considered to have not completed a fasting state. The investigator will assess for skin reaction at the sensor site. Participants will be asked about their experience and acceptability of blinded CGM. Participants will be encouraged to undergo the standard of care 6-12 week postpartum OGTT. Participants will be provided with another sensor to be placed before OGTT, and application will be reviewed.

Visit 4: Visit 4 will be conducted remotely. Participants will be contacted by text or phone call to encourage them to undergo the standard of care OGTT. If a participant is unable to have an OGTT performed through her normal care, she can have an optional in-person visit to have it performed at the study site. All participants will be instructed to place a Dexcom sensor at least 48 hours prior to their planned OGTT.

Home use: Participants will wear the sensor for at least 48 hours before planned OGTT for a total of ten days or less if there is a sensor failure or the device is dislodged. After ten days, the participant will remove the sensor.

Visit 5: Visit 5 will be conducted remotely after the 6-12 week OGTT. Participants will be instructed to mail the sensor back to the study team in pre-addressed, prepaid packaging. The investigator will assess for skin reaction at sensor site. Participants will be asked about their experience and acceptability of OGTT testing. Results of the OGTT will be recorded. If it is performed at an outside facility, the participant will request that the records be shared with the research team. Results of CGM data may be shared with a participant and her providers if requested by the participant after her routine OGTT. Investigators will not provide results before this to decrease risk of participants not completing the standard of care OGTT.

5 STUDY POPULATION

5.1 TARGET ENROLLMENT

50 participants

5.2 INCLUSION CRITERIA

Pregnant or delivered within the past 3 days

Diagnosis of gestational diabetes during current pregnancy

Age 18 or older

5.3 EXCLUSION CRITERIA

Pregestational diabetes

Known skin adhesive allergy

Chronic steroid use which will be ongoing after hospital discharge

5.4 LIFESTYLE CONSIDERATIONS

Trends in use of telehealth have been incorporated into this protocol to accommodate maximum number of participants.

5.5 SCREEN FAILURES

If participant meets an exclusion criteria after enrollment, such using steroids, their data will not be included in analysis.

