1 PROTOCOL SUMMARY

1.1 SYNOPSIS

Title:	Postpartum dysglycemia screening with continuous glucose monitoring
Study	Gestational diabetes (GDM) is one of the most common complications of pregnancy, and up to one third of women with GDM will have abnormal blood sugars after their pregnancy. To screen for abnormal blood sugars, standard of care is a 6-12 week postpartum oral glucose tolerance test (OGTT). However only 17-60% of women actually have this test performed. This study is to assess the feasibility of using a continuous glucose monitor placed on discharge from the hospital after delivery as a screening method to detect postpartum abnormal blood sugars.
Description:	
Objectives:	
Primary Objective: To assess the feasibility of continuous glucose monitoring compared to oral glucose tolerance testing for the diagnosis of postpartum diabetes in women with recent gestational diabetes.
 
Secondary Objectives: To evaluate the specificity, sensitivity, positive predictive value, and negative predictive value of continuous glucose monitoring compared to oral glucose tolerance testing for the diagnosis of postpartum dysglycemia in women with recent gestational diabetes.
 
To evaluate the influence of predictors of lack of postpartum oral glucose tolerance testing on completion of postpartum continuous glucose monitoring.

Endpoints:	
Primary Endpoint: Percentage of participants with at least 72 hours of CGM data downloaded.
 
Secondary Endpoints: CGM acceptability scoring Specificity, sensitivity, PPV, and NPV for CGM compared to OGTT will be performed for diagnosis of DM, IGT, and IFG

Study Population:	Pregnant or recently pregnant women who were diagnosed with GDM during current/recent pregnancy. Target enrollment: 50 participants
Sites/Facilities Enrolling Participants:	Icahn School of Medicine at Mount Sinai

[figure not shown]

Description of Study Intervention: Women will be consented and screened before or after delivery. They will be asked about medical history, medications, and diabetes risk factors. A Dexcom Professional CGM will be placed on postpartum day 1-3. Participants will wear the sensor for 10 days and return it at their postpartum visit or by mail. They will be given another sensor to place before their standard of care OGTT and will mail the sensor back after that test is performed.

Study Duration: 1 years

Participant Duration: Up to 20 weeks

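### The steroid example in section 5.5 is broader than the exclusion criterion it illustrates, and the rule has no cut-off at sensor placement and no endpoint limit

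*Combined protocol and SAP*

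**What the plan says.** - Section 5.5 (Screen failures) is one sentence: "If participant meets an exclusion criteria after enrollment, such using steroids, their data will not be included in analysis". It gives no end date and does not say which analysis is meant.
- Section 5.3 lists the steroid criterion as "Chronic steroid use which will be ongoing after hospital discharge". Section 4.1 (Visit 1) adds that the continuation past discharge is a planned one.
- Women may be "consented at their obstetrics or endocrinology visits during their third trimester or during admission for delivery", and the synopsis says "A Dexcom Professional CGM will be placed on postpartum day 1-3" (4.1 also allows day 0). Weeks can therefore pass between enrolment and the first sensor.
- At Visit 2 women are asked about "steroid administration within the past week". No later steroid question appears in the visit descriptions, although the questionnaire content is not given.
- Section 8.2.4 plans an analysis that drops glucose readings taken too soon (four half-lives) after the latest steroid dose. It drops readings, not women. Section 3 explains that this should show whether steroid exposure has to be taken into account when CGM is used.
- Sections 8.2.1 and 8.2.3 report the 72-hour feasibility result and skin reactions as percentages of participants. Neither defines an analysis set.
- Section 6.1 withdraws women unwilling or unable to wear the device for 72 hours, and lets a woman with a skin reaction stay in once she has 72 hours of data.

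**The concern.** Two things are wrong with the rule as written.

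First, its example does not match its criterion. A short course around delivery is steroid use, but it is not chronic use planned to continue past discharge. If the example governs, section 5.5 discards whole women, while section 8.2.4 assumes that they remain and that only some of their readings are set aside.

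Second, one undivided exclusion is applied to endpoints that have different needs. Steroids can distort glucose values, so there is a case for handling them in the accuracy analyses. They have no bearing on whether 72 hours of data were downloaded, and the plan gives no reason to discard a skin-reaction result because of them. With no cut-off, a removal could also be decided after a woman's CGM or OGTT results are known. Two analysts could then report different primary percentages from the same data.

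**Working it through.** The target of 50 (section 5.1) rests on precedent (section 8.1). No inputs are stated, so there is no calculation to reproduce. The check is mainly a comparison of texts.

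**Step 1. Who is removed under each reading of 5.5**

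| Woman | Criterion in 5.3 and 4.1 | Example in 5.5, as worded | Expected by 8.2.4 |
|---|---|---|---|
| Chronic use, planned to continue past discharge | Removed | Removed | Not addressed |
| Short course around delivery, given after consent | Kept | Removed | Kept, early readings dropped |
| Same short course, given before consent on the postpartum floor | Kept | Not reached, because exposure precedes enrolment | Kept, early readings dropped |

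The second row is the conflict. The second and third rows together show that, on the broad reading, the same exposure is treated differently according to the date of consent.

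**Step 2. Which endpoints are affected.** Section 5.5 removes data from analysis without qualification, and 8.2.1 and 8.2.3 define no set that would override it. A woman removed after placement therefore leaves both percentages.

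**Step 3. Illustrative size.** The documents give no rate of removal, so all counts below are assumed. If k women are dropped from x successes in n = 50, the result is x/(50 − k) when all were failures and (x − k)/(50 − k) when all were successes. Intervals are exact (Clopper-Pearson) 95%.

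- Feasibility, no removal: 40/50 = 80.0% (66.3 to 90.0).
- k = 1: 40/49 = 81.6% or 39/49 = 79.6%.
- k = 2: 40/48 = 83.3% or 38/48 = 79.2%.
- k = 5: 40/45 = 88.9% or 35/45 = 77.8%.
- Skin reactions, no removal: 5/50 = 10.0% (3.3 to 21.8).
- k = 1: 4/49 = 8.2% if she had a reaction, 5/49 = 10.2% if not.
- k = 5: 0/45 = 0% if all five had reactions, 5/45 = 11.1% if none had.

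With one or two women removed, feasibility moves by at most 83.3 − 80.0 = 3.3 points, against an interval 90.0 − 66.3 = 23.7 points wide. The extreme skin-reaction result at k = 5 requires every removed woman to have had a reaction, and nothing in the documents suggests that.

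**Step 4. Accuracy.** At the planned 50% OGTT completion (section 5.6), 50 × 0.5 = 25 women have a reference result. At the cited upper figure of one third abnormal (section 2.1), 25/3 is about 8 cases. If 6 of 8 are detected (assumed), sensitivity is 75.0%. Dropping one missed case gives 6/7 = 85.7%, and dropping one detected case gives 5/7 = 71.4%. This pools DM, IGT and IFG, which 8.2.2 lists separately. The instability comes mostly from having so few cases, not from 5.5 itself.

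**The case against.** The best defence is that 5.5 is a screen-failure rule and should be read as one. Its heading says so, it applies only to women who meet a criterion, and the criterion concerns a plan judged around discharge. Section 2.2 has the sensor placed on discharge, so eligibility is normally settled by about the time of placement. The described medication and steroid questions come at Visits 1 and 2, which fits a rule meant to stop there. Removing women who become ineligible between consent and placement is ordinary practice. The study is also a descriptive pilot with no success threshold. All of this stands, and it is why the point is minor. It does not remove the mismatch between the example and the criterion, and it supplies a cut-off that the text does not state.

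A reader might infer two stronger points, and the documents support neither.

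- *That any woman who starts steroids weeks later loses a primary result already fixed.* The timeline looks persuasive: placement by day 3; "Participants will wear the sensor for ten days or less if there is a sensor failure or the device is dislodged", so off by day 13; "mail the sensor to the study team within thirty days of placement", so due by day 33; and "Visit 5 will be conducted remotely after the 6-12 week OGTT", so up to day 84. That leaves 84 − 33 = 51 days. But steroids first started then meet the criterion only if the loose example is read to override it. The primary endpoint is also not expressly limited to the first sensor, so a result settled by day 33 is an assumption.
- *That a woman whose adhesive allergy first shows on the study sensor is removed, together with her reaction.* Section 5.3 requires a known allergy, and 6.1 lets a woman with a reaction continue once she has 72 hours of data. That largely answers the point.

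**Conclusion.** The concern holds as a minor drafting fault with two parts. The firm part is the inconsistency between the 5.5 example and sections 3, 5.3, 4.1 and 8.2.4: they cannot all be followed for a woman given a short steroid course after consent. The second part is the missing cut-off and endpoint limit, which lets a removal after placement reach the feasibility and skin-reaction percentages.

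The direction of any effect depends on who is removed: dropping a failure raises feasibility, and dropping a success lowers it. The size cannot be estimated from the documents. If one or two women are affected, the shift is well below sampling error at n = 50. That rests on assumed counts and on the expectation, which the documents do not quantify, that few women would be removed. The accuracy estimates are more sensitive to a single removal. This has some weight because section 8.1 intends the secondary outcomes to inform the power calculations of a later study.

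**What to change.** 1. Reword the example in 5.5 to match the 5.3 criterion, so that short peripartum exposure is handled only by the 8.2.4 analysis.
2. Limit 5.5 to ineligibility present or arising before the first sensor is placed, judged without knowledge of CGM or OGTT results, and report the number removed.
3. In 8.2.1 and 8.2.3, compute the feasibility and skin-reaction percentages on all women with a sensor placed. Count women withdrawn under 6.1 before 72 hours as feasibility failures. Report separately how many enrolled women never had a sensor placed.
4. Confine any steroid-based removal after placement to the accuracy analyses, and report those measures with and without the women concerned.

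The cost is one paragraph in 5.5 and one line each in 8.2.1 and 8.2.3, with no extra visits or participants. Item 4 covers only steroid use that comes to the team's attention; a steroid question at Visits 3 and 5 would make this systematic, but it is optional. The downside is that the feasibility and skin-reaction figures may look slightly less favourable.

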5.6 STRATEGIES FOR RECRUITMENT AND RETENTION

Since up to 40% of women do not attend any postpartum visits [11], our study recruitment and retention will need to be optimized. Participants will be recruited from their routine obstetrics and endocrinology visits and also from the postpartum labor and delivery floor. Consent will be translated into Spanish, and interpreters will be used to increase potential recruitment and recruit a more diverse and representative study population. We believe the availability of remote visits will decrease burden on participants, will increase retention for women who do not wish attend postpartum visits, and will address potential limitations on research visits at study sites due to COVID-19 concerns. The option for visit 2 to be performed either on the postpartum floor or remotely will allow recruitment of women who are delivering at multiple locations.

Compensation will be provided for time and effort. Participants will receive \$25 after Visit 1, \$75 after Visit 3 and an additional \$125 after completion of their standard OGTT. We estimate that 50% of participants will complete their standard OGTT with reminders and incentives; the enrollment goals have been planned accordingly.

6 STUDY INTERVENTION DISCONTINUATION AND PARTICIPANT DISCONTINUATION/WITHDRAWAL

6.1 DISCONTINUATION OF STUDY INTERVENTION

Participants will be withdrawn from the study without their consent if the participant indicates they are not willing or not able to wear the study device for at least 72 hours. If participant has an adverse skin reaction but have collected 72 hours of data, they can continue in the study and may forego the second CGM placement if they prefer.

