6.2 PARTICIPANT DISCONTINUATION/WITHDRAWAL FROM THE STUDY

Participants can withdraw from the study at any time if they so wish. If a participant decides to withdraw their permission and disclosure of their Protected Health information from the study, she will need to do so in writing to the principal investigator [name] [name].

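### Section 6.1 withdraws women who say they will not or cannot wear the sensor for 72 hours from the whole study, so their acceptability answers and OGTT follow-up are likely to be lost

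*Combined protocol and SAP*

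**What the plan says.** Section 6.1 is headed as discontinuation of the intervention, but its rule concerns the study: "Participants will be withdrawn from the study without their consent" if they indicate they are "not willing or not able to wear the study device for at least 72 hours". For a participant with an adverse skin reaction, the next sentence adds: "but have collected 72 hours of data, they can continue in the study and may forego the second CGM placement if they prefer".

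The follow-up at issue is described in section 4.1:

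- **Visit 2:** "Participants will be asked for permission for access to review and record their future OGTT results".
- **Visit 3:** "Participants will be asked about their experience and acceptability of blinded CGM". The skin assessment is also done here.
- **Visit 4:** "Participants will be contacted by text or phone call to encourage them to undergo the standard of care OGTT". A woman who cannot get the test through her usual care is told that "she can have an optional in-person visit to have it performed at the study site".
- **Visit 5:** the OGTT result is recorded.

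The home-use paragraph of 4.1 treats sensor failure or dislodgement as a shorter period of wear and mentions no withdrawal. Under 6.2, a woman may leave at any time. To withdraw permission for her health information, "she will need to do so in writing to the principal investigator". Section 5.5 drops from analysis the data of women who meet an exclusion criterion after enrollment. Section 8.2.1 gives the primary analysis in one line, as the percentage of participants with 72 hours or more of downloaded data. It does not define the denominator further.

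**The concern.** In a feasibility study, women who decline or give up the device are part of the result. Section 6.1 ends their participation for indicating that they will miss the threshold the study measures.

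Two listed items need data from them. The first is the secondary endpoint of CGM acceptability. A woman who was fitted with a sensor and stopped early can say most about what makes it unacceptable. The second is the exploratory analysis in section 3 of whether similar populations complete CGM and OGTT. It needs OGTT completion from women who did not complete CGM. If those women also lose the reminder and the recording of the result, the comparison is thinnest where it should be most informative.

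**Working it through.** **Step 1. Who is affected.**

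| Situation | Where | Stays in the study? |
|---|---|---|
| Skin reaction, 72 hours of data already collected | 6.1, second sentence | Yes, second sensor optional |
| Wear shortened by sensor failure or dislodgement | 4.1, home use | Yes, no withdrawal mentioned |
| Woman indicates she will not or cannot wear it for 72 hours | 6.1, first sentence | No |

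Only the last row is affected. Whether failure or dislodgement could also count as not being able to wear the device is unclear from the text. The first row shows that the plan already accepts follow-up without further sensor wear.

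**Step 2. What follow-up remains.** The schedule of activities, 4.1, 5.5, 6.1 to 6.3 and 8.2 contain no provision for acceptability, skin assessment, OGTT reminder or OGTT recording after a 6.1 withdrawal. Section 6.3 only repeats the expected 50% OGTT completion. Record look-up may remain possible for women who gave permission at Visit 2. Women withdrawn before Visit 2 would not yet have been asked.

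**Step 3. Size of the follow-up loss.** Target enrollment is 50 (section 5.1). The documents give neither w, the number of 6.1 withdrawals, nor s, the number reaching 72 hours; both are assumed here. Share of all women = w/50. Share of CGM non-completers = w/(50 − s).

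| w | w/50 | s = 40 (10 non-completers) | s = 45 (5 non-completers) |
|---|---|---|---|
| 1 | 2% | 1/10 = 10% | 1/5 = 20% |
| 2 | 4% | 2/10 = 20% | 2/5 = 40% |
| 5 | 10% | 5/10 = 50% | not shown |

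If these women completed the OGTT at the plan's 50% rate (sections 5.6 and 6.3), w = 2 would mean 2 × 0.5 = 1 OGTT result and w = 5 would mean 2.5. For the completion comparison, the missing item is completion status, yes or no, for all w women.

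**Step 4. Primary percentage.** The natural denominator is all enrolled women less 5.5 exclusions, with 6.1 cases counted as not reaching 72 hours. Taking no 5.5 exclusions, the result is s/50 and the bias is 0. Only if 6.1 cases were dropped would it become s/(50 − w). With s = 40, 40/50 = 80.0% would become 40/49 = 81.6%, 40/48 = 83.3% or 40/45 = 88.9% for w = 1, 2 or 5. Even 88.9% lies inside the exact 95% interval for 40/50, which is 66.3% to 90.0%.

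**The case against.** The strongest reply is that the loss is inferred from silence. The plan does not say that these women's data are discarded or that contact ends. OGTT permission is sought at Visit 2, 6.2 requires written notice to revoke permission, and 7.1.2 follows adverse events after discontinuation. The consent pages are not in the reviewed copy and might cover follow-up after withdrawal. This stands: the loss is likely, not certain.

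The affected group may also be small, and some women may decline before any sensor is placed. They have no wear to rate, so acceptability loses nothing from them. This also stands. The acceptability point applies only to women already fitted with a sensor, and the counts above do not separate the two groups.

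Three stronger readings are tempting, but the documents do not support them.

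- **All women short of 72 hours lose follow-up.** The home-use text in 4.1 lets failure or dislodgement shorten wear without withdrawal.
- **The primary percentage is inflated.** Section 5.5 expressly removes data from analysis and 6.1 does not, so the ordinary meaning of a percentage of participants keeps 6.1 cases in. The study is a descriptive pilot with no success threshold.
- **The accuracy estimates are damaged.** These women have little or no CGM data, so sensitivity, specificity, PPV and NPV hardly change. Demographic predictors are already recorded at Visit 1.

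The objection does not remove the central point. Followed as written, 6.1 takes these women out of the study, and no visible text brings them back for the two items that need them.

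**Conclusion.** The point holds in a limited form and is a cheap improvement. The wording that withdraws these women from the study is explicit. Confidence that their follow-up is lost is moderate, because it rests on the absence of a provision, on consent pages not seen, and on possible record look-up.

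The harm is selective missingness in one secondary endpoint (acceptability, for women fitted with a sensor) and one exploratory comparison (CGM against OGTT completion). Its size cannot be derived from the documents. The illustrative range is 2% to 10% of all women for 1 to 5 withdrawals, or 10% to 50% of non-completers if 40 of 50 reach 72 hours. The denominator needs confirmation only, and on the natural reading no result changes.

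**What to change.** 1. **In 6.1, separate stopping the device from leaving the study.** Leave the decision to stop wearing the sensor as it is. Keep these women in follow-up for OGTT completion and result, and for the acceptability questions and skin assessment if a sensor was placed, unless they withdraw under 6.2. State whether failure or dislodgement before 72 hours falls under this rule.
2. **In 8.2.1, as confirmation only, state the denominator:** all enrolled women less 5.5 exclusions, with 6.1 cases counted as not reaching 72 hours. Report the numbers under 5.5 and 6.1.

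The cost is protocol wording, a few contacts and questionnaires, and OGTT record look-ups. Section 5.6 pays $75 after Visit 3 and $125 after the OGTT, so payments are at most $75 + $125 = $200 per retained woman: $400 for two and $1,000 for five. Some may use the optional study-site OGTT, whose cost, like that of staff time, the documents do not give. There is also the burden of contacting women who have turned down the device. Some will decline, so the gap may shrink rather than close.
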